5.8.3 Other Secondary Efficacy Endpoints

Other secondary endpoints include EFS, DOR, and duration of skin response. EFS is defined as the time from randomization until any cause of treatment failure: PD, discontinuation of treatment for any reason, or death due to any cause, whichever occurs first. DOR in subjects with a confirmed response is the time between first documentation of response and PD. Duration of skin response is the time between the first skin response and PD in skin.

5.8.3.1 Other Secondary Efficacy Analysis

The ITT principle will be used to determine the event time or censoring time for the EFS analysis. Disease assessment data should be collected according to the intended schedule of assessment, and the date of progression should be assigned based on the time of the first documentation of PD regardless of violations or discontinuation of study drug.

For EFS, patients who are lost to follow-up will be censored at last disease assessment. Patients who withdraw consent or start new antineoplastic therapy will be treated as if experiencing an EFS event. Patients without baseline and/or sufficient post baseline data for disease assessment and no treatment discontinuation or death recorded will be censored at the date of randomization. Analyses of EFS will be performed based on the ITT population.

DOR will be analyzed for the subgroup of patients with confirmed response (CR or PR) in the ITT population. Patients who are lost to follow-up, withdraw consent, or discontinue treatment due to undocumented PD after the last adequate disease assessment will be censored at the last disease assessment. If the patient starts new antineoplastic therapy before PD, the patient is treated as progressed at the date of assessment at which PD was documented.

Duration of skin response will be analyzed for the subgroup of patients with skin response (CR or PR in skin) in the ITT population. Patients who are lost to follow-up, withdraw consent, or discontinue treatment due to undocumented PD in skin after the last adequate skin assessment will be censored at the last skin assessment. Patients without sufficient skin assessment data after the initial skin response and with no death recorded will be censored at the date of the initial skin response. If the patient starts new antineoplastic therapy before skin PD, then the patient is treated as progressed at the date of the skin assessment at which PD in skin was documented.

EFS will be analyzed similarly as the key secondary efficacy endpoint PFS as described in Section 5.8.1. DOR and duration of skin response will be summarized descriptively using the Kaplan-Meier method.

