7.7 Discontinuation of Treatment With Study Drug, and Patient Replacement

Study drug should be discontinued for patients meeting any of the following criteria:

- Completed 16 cycles of brentuximab vedotin therapy or 48 weeks of reference therapy
- Progressive disease

The reason justifying study treatment withdrawal should be documented in the eCRF.

Patients who discontinue from study treatment will remain on study for follow-up unless they withdraw consent for the follow-up phase of the study. All randomized patients will be followed until study closure (see Section 7.6).

Patients who are randomized to a treatment arm but do not receive study drug for any reason will not be replaced. Additional patients may be enrolled to ensure an adequate number of evaluable patients in the study, ie, approximately 124 patients in the ITT population.

Treatment with study drug may also be discontinued for any of the following reasons:

- Adverse event
- Protocol violation
- Study terminated by sponsor
- Withdrawal by subject
- Lost to follow-up

- Other

Once study drug has been discontinued, all study procedures outlined for the End of Treatment visit will be completed as specified in the Schedule of Events. The primary reason for study drug discontinuation will be recorded on the eCRF.

A “real-time” independent review of disease status will be performed at the time of treatment discontinuation for all patients. In the event of suspected progressive disease, investigators will be encouraged to await the results of the independent review that may indicate or confirm progression in GRS before recommending to the patient any treatment or management options, such as discontinuation from study drug treatment to pursue alternative anticancer therapy.

Note that some patients may discontinue study drug for reasons other than progressive disease before completing the full treatment course; these patients will remain in the study for posttreatment assessments as outlined in the [Schedule of Events](#).

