Other secondary efficacy endpoints include EFS, duration of response, and duration of skin response. EFS is defined as the time from randomization until any cause of treatment failure: disease progression, discontinuation of treatment for any reason, or death due to any cause, whichever occurs first. Duration of response in subjects with confirmed response is the time between first documentation of response and disease progression. Duration of skin response is the time between the first skin response to progressive disease in skin. Stratified log-rank test statistics will be used to compare EFS between the 2 treatment arms. The hazard ratios along with the 95% CIs will be estimated using a stratified Cox regression model. The Kaplan-Meier method will be used to estimate the distribution of EFS for each treatment. Median times (if estimable), along with the 2-sided 95% CIs will be presented. Duration of response and duration of skin response will be summarized descriptively using the Kaplan-Meier method.

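### EFS: a patient lost to follow-up while on study treatment is an event under the definition but censored under SAP 5.8.3.1

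*SAP*

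**What the plan says.** **Definition.** SAP 5.8.3: "EFS is defined as the time from randomization until any cause of treatment failure: PD, discontinuation of treatment for any reason, or death". Protocol 8.1.6.2 has the same components: "disease progression, discontinuation of treatment for any reason, or death due to any cause, whichever occurs first". Neither makes an exception for loss to follow-up.

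**Reasons for stopping.** Protocol 7.7 opens its list with "Treatment with study drug may also be discontinued for any of the following reasons". One entry is "Lost to follow-up"; withdrawal by the patient is a separate entry. The section also requires the primary reason to be entered on the eCRF.

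**Event and censoring rules in SAP 5.8.3.1.**
- Loss to follow-up: "For EFS, patients who are lost to follow-up will be censored at last disease assessment".
- Withdrawal of consent and new therapy: "Patients who withdraw consent or start new antineoplastic therapy will be treated as if experiencing an EFS event".
- Insufficient disease assessment data: patients with "no treatment discontinuation or death recorded will be censored at the date of randomization".

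SAP section 6 declares no departure from the protocol's planned analyses.

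**The concern.** The definition and the censoring rule give opposite answers for one identifiable group: patients whose treatment ends because contact is lost. Two programmers could each follow the SAP and build different EFS datasets. The choice matters because EFS is compared between arms with a stratified log-rank test and a stratified Cox model. Censoring these patients treats a component of the endpoint as non-informative missingness. The trial is open-label, so similar loss in the two arms cannot be taken for granted.

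No planned analysis would show the effect. SAP 5.8.3.1 says EFS is handled like PFS, and none of the PFS sensitivity analyses in SAP 5.8.2.1.1 varies the treatment of loss to follow-up.

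**Working it through.** The plan gives no EFS event count, hazard ratio or power, so there is no figure to reproduce. The main check compares the rules.

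**Step 1: rules side by side**

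| Patient | Definition (SAP 5.8.3, Protocol 8.1.6.2) with Protocol 7.7 | SAP 5.8.3.1 |
|---|---|---|
| Withdraws consent on treatment | Event | Event |
| Lost to follow-up on treatment | Event | Censored at last disease assessment |
| Stops for toxicity, lost later | Event at the stop | Event already fixed by the definition |
| Completes planned course, then lost without PD | Depends on whether completion is a discontinuation | Censored |

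Only the second row is a contradiction. The fourth is a gap: Protocol 7.5 calls 16 cycles or 48 weeks completion of treatment, while Protocol 7.7 lists the same milestone among the criteria for discontinuing study drug. Read literally, 7.7 would turn every completer into an EFS event.

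**Step 2: patients affected**

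Inputs: N = 124 and 10% dropout (SAP 5.1). The 10% covers all causes and was set for the sample size of the primary endpoint. The share lost on treatment, f, is an assumption.

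- f = 2%: 0.02 × 124 = 2.48, about 2
- f = 5%: 0.05 × 124 = 6.2, about 6
- f = 10%: 0.10 × 124 = 12.4, about 12

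**Step 3: illustrative effect on the hazard ratio**

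Assumptions: exponential times, with the PFS medians of 9 and 6 months (SAP 5.8.2.1.2) standing in for EFS.

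- Brentuximab vedotin: h_B = ln 2 / 9 = 0.0770 per month
- Control: h_C = ln 2 / 6 = 0.1155 per month
- Losses censored: HR = h_B / h_C = 6/9 = 0.667
- Balanced losses counted as events: add a common hazard λ = [f / (1 − f)] × (h_B + h_C) / 2, so HR = (h_B + λ) / (h_C + λ)

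| f | λ | HR with losses as events |
|---|---|---|
| 2% | 0.0020 | 0.672 |
| 5% | 0.0051 | 0.681 |
| 10% | 0.0107 | 0.695 |

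For f = 10%: (0.0770 + 0.0107) / (0.1155 + 0.0107) = 0.0877 / 0.1262 = 0.695.

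**Outer limit, not a forecast.** If all losses at f = 10% fell in one arm, 20% of that arm would be lost. The hazard ratio would be 0.667 / 0.8 = 0.833 if that arm were brentuximab vedotin and 0.667 × 0.8 = 0.533 if it were control.

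**The case against.** **The censoring sentence is a specific rule that qualifies a general definition.** It is written for EFS alone, so this reading is possible. Neither document states it, however, and SAP section 6 declares no change from the protocol. The insufficient-data rule in the same paragraph is conditioned on there being no recorded treatment discontinuation, which suggests that a recorded discontinuation is meant to count. The objection shows that precedence is unstated; it does not remove the conflict.

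**Withdrawal and loss are different events.** Withdrawal is an active decision with a known date, while loss leaves status and timing uncertain. Treating them differently could be defended, and the inconsistency with consent withdrawal is supporting evidence only. But the definition covers any reason for stopping and draws no such line. The uncertain date is a fair point that the fix has to deal with.

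**A reader might infer that every patient lost to follow-up is censored, including one who had already stopped for toxicity.** The documents do not support this. The definition ends "discontinuation of treatment for any reason, or death due to any cause, whichever occurs first", which fixes the earlier event. The PFS rule in SAP 5.8.2.1.1 is worded the same way, and nobody would take it to cancel a documented progression.

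**A reader might also infer that a whole 10% dropout becomes lost events and biases one arm's hazard by a similar share.** That is not supported either. The 10% is not a loss-to-follow-up rate, dropouts who withdraw consent are already events, no EFS event count is projected, and nothing in the documents indicates that losses would concentrate in one arm.

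**Conclusion.** The contradiction is real but confined to patients lost to follow-up while on study treatment. The direction of any bias cannot be established from the documents.

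The size rests on an assumed loss rate. About 2 to 12 of 124 patients would change status for rates of 2% to 10%, the upper end being a ceiling if the planning dropout holds. With balanced losses the effect on the hazard ratio is small (at most 0.667 to 0.695 in the illustration); it would be larger with unequal losses. The illustration also depends on exponential times and on PFS medians standing in for EFS.

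EFS is an other secondary endpoint outside the weighted Holm procedure of SAP 3.2. The primary test, the key secondary tests and the sample size are unaffected. This is a low-severity point, worth correcting because the correction is cheap.

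**What to change.** Amend SAP 5.8.3.1 as follows:

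1. Treatment discontinuation with loss to follow-up as the recorded reason is an EFS event, in line with the definition.
2. Specify its date: for example the recorded discontinuation date, or the last dose date where the former is only administrative.
3. Limit censoring for loss to follow-up to patients with no prior EFS event who are not on treatment.
4. State that completing the planned 16 cycles or 48 weeks is not a discontinuation event. Without this, item 3 would apply to almost no treated patient.
5. Add one sensitivity analysis that censors on-treatment losses at the last disease assessment, and report the number of such patients by arm.

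The cost is SAP wording and one extra EFS run. The reason for discontinuation is already collected on the eCRF, so no new reason field is needed.

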5.9 Pharmacokinetic, Pharmacodynamic, and Biomarker Analysis

5.9.1 Pharmacokinetic Analyses

The PK of the antibody drug-conjugate (brentuximab vedotin), total antibody, and unconjugated drug (MMAE) will be derived from serum concentration versus time data for all patients who met study inclusion criteria, received study drug, and provided evaluable PK data. Population PK parameters will be calculated with an appropriate method based on a validated PK analysis program.

CCI

5.9.2 Pharmacodynamic Analyses

Absolute and change from baseline values of circulating pharmacodynamic biomarkers such as soluble CD30 (sCD30), thymus and activation regulated chemokine (TARC or CCL17), and CTACK (CCL27) will be summarized by time point using descriptive statistics (e.g., number of patients, mean, standard deviation, median, minimum, maximum), as applicable. Descriptive statistics will also be provided to summarize biopsy pharmacodynamic parameters, such as pHisH3, and change from baseline values, as applicable.

5.9.3 Immunogenicity Analysis

All patients who were administered at least 1 dose of brentuximab vedotin will be evaluated for antitherapeutic antibody (ATA) development. A list/table of ATA status will be provided. Antibody neutralizing status (neutralizing or not neutralizing) will also be listed for patients who have positive antibody status.

Immunogenicity information, including ATA and neutralizing ATA, will be summarized in descriptive statistics as applicable.

The relationship between antibody status and efficacy and/or safety will be explored.

5.9.4 Biomarker Analysis

5.10 Analyses of Patient-Reported Outcomes and Health Economics

PRO endpoints include subscales of Skindex-29 and global and subscale scores of the EQ-5D and FACT-G questionnaires. The health economic endpoint includes medical resource utilization (MRU) enumerations. Furthermore, the symptom domain of Skindex-29 is one of the key secondary endpoints. Its analysis is described separately in Section 5.8.2.1.2. The analyses of the remaining PRO and MRU endpoints and the additional analysis of Skindex-29 symptom scores are described below.

Analyses of PROs and health economics will be performed using the ITT population.

5.10.1 Patient-Reported Outcomes Analysis

All PRO scores will first be scaled into numeric scores following published or prespecified scoring guidelines for each PRO instrument employed in this trial. The maximum allowed number of missing items to adequately measure a domain is instrument specific and found in the relevant guidelines. Missing pattern of PRO data (noncompliance, missing, dropout) will be examined and summarized. Additional imputation methods, such as last observation carried forward, or multiple imputation may be considered if appropriate.

For Skindex-29 (global, symptoms, emotions, and functioning), EQ-5D (global, EQ-5D descriptive system and the EQ visual analogue scale), and FACT-G (global, physical well-being, social/family well-being, emotional well-being, and functional well-being), scores will be summarized in descriptive statistics for the 2 treatment groups over time.

5.10.2 Health Economics Analysis Using Medical Resource Utilization

MRU data are collected through the medical encounter page of the eCRF.

MRU data will be summarized in descriptive statistics of hospitalization (length of stay, inpatient, outpatient, and reason), number of missing days from work or other activities by subject, and care-giver for the 2 treatment groups.

5.11 Safety Analyses

Safety evaluations will be based on the incidence, severity, type of adverse events (AEs), clinically significant changes, or abnormalities in the subject's physical examination, vital signs, ECOG performance status, and clinical laboratory results.

These analyses will be performed using the safety population.

5.11.1 Adverse Events

5.11.1.1 Adverse Events

Treatment-emergent AEs (TEAEs) will be tabulated by primary System Organ Class (SOC), High Level Term (HLT), and Preferred Term (PT). A TEAE is defined as any AE that occurs after administration of the first dose of study drug and up through 30 days after the last dose of study medication. AEs will be tabulated according to the most recent version (Version 8.1 or higher) of the Medical Dictionary for Regulatory Activities (MedDRA) by SOC, HLT, and PT and will include the following categories:

- TEAEs
- Study drug-related TEAEs
- Grade 3 or higher TEAEs
- Grade 3 or higher drug-related TEAEs
- TEAEs resulting in study drug discontinuation
- Serious AEs (SAEs), including study drug-related SAEs
- AEs of peripheral neuropathy identified by the broad search MedDRA SMQ "Peripheral neuropathy"

Additional analyses of peripheral neuropathy may also be presented.

The most commonly reported TEAEs (i.e., those events reported by $\geq 10\%$ of all patients) will be tabulated by HLT and PT.

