4.3 Duration of Study

Patients who achieve a response (CR or PR) may receive brentuximab vedotin up to 16 cycles (48 weeks) or reference therapy for up to 48 weeks. Patients with stable disease may continue therapy (maximum 16 cycles brentuximab vedotin or 48 weeks reference therapy) at the discretion of the investigator. For all patients who complete either 48 weeks of dosing in the control arm or 16 cycles of brentuximab vedotin, an attempt to discontinue therapy should be made following EOT. For patients who complete 48 weeks of reference therapy, initiation of subsequent standard-of-care therapy should be discussed with the study sponsor. For patients who complete 16 cycles of brentuximab vedotin, access to brentuximab vedotin may be permitted in accordance with local regulatory requirements and at the joint discretion of the sponsor and investigator.

To permit the detection of any delayed treatment-related AEs, patients will be followed for 30 days after the last dose of study medication. Posttreatment assessments of disease response will be conducted every 12 weeks for a minimum of 24 months after EOT, and then every 6 months; or until progressive disease or study closure. All randomized patients will also be followed for survival every 12 weeks for a minimum of 24 months after the

Brentuximab vedotin (SGN-35)**Clinical Study Protocol C25001 Amendment 5, EudraCT: 2010-024215-14**

EOT visit, then every 6 months until patient withdrawal, death, or study closure.

Information may be collected by phone for patients with progressive disease.

The final analyses for the clinical study report will be performed 10 months after the last patient is enrolled (ie, approximately 34 months from the start of study). The updated analyses on the efficacy endpoints will be conducted after all patients enrolled in the study have had the opportunity to complete 16 cycles of treatment with brentuximab vedotin or 48 weeks of treatment with reference therapy and 24 months of posttreatment follow up, and will be included in an addendum to the clinical study report.

The total study duration will be approximately 5 years, including an anticipated enrollment duration of 24 months.

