1.1 Study Design

This is an open-label, randomized, multicenter study. All patients must have histologically-confirmed CD30-positive (CD30+) cutaneous T-cell lymphoma (CTCL) by central laboratory assessment and pathology review. Patients are to be stratified by diagnosis: primary cutaneous anaplastic large cell lymphoma (pcALCL) or mycosis fungoides (MF), and randomized to treatment with brentuximab vedotin monotherapy (Arm 1) up to 16 cycles total (48 weeks), or methotrexate (MTX) or bexarotene per physician's choice (Arm 2) up to a total of 48 weeks.

Objective response, lasting at least 4 months (ORR4), per independent review facility (IRF) will be assessed by global response score (GRS), which consists of skin evaluation (mSWAT assessment), nodal and visceral radiographic assessment, and detection of circulating Sézary cells (MF only). Complete response (CR) or partial response (PR) per GRS will be confirmed by sustained response in skin per mSWAT assessment at the subsequent cycle. All randomized patients will be followed for survival every 12 weeks for a minimum of 24 months after the EOT visit, and then every 6 months until patient withdrawal, death, or study closure.

Patients with a documented PR or CR at the end of Cycle 3 and at any disease assessment thereafter may continue treatment with study drug for up to 16 cycles with brentuximab vedotin or 48 weeks with bexarotene or methotrexate; patients with stable disease may continue therapy at the discretion of the investigator. Patients with progressive disease (PD) at any time during the study will be discontinued from study treatment. Patients with increasing mSWAT before assessment at the end of Cycle 3 will be allowed to continue therapy until the Cycle 3 assessment if, in the investigator's opinion, the findings are due to tumor flare rather than disease progression.

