5.1 Sample Size Justification

Approximately 124 patients (approximately 62 patients per treatment arm) will be randomized to the study (124 patients are targeted for the ITT population). The sample size was calculated to provide 90% power to detect a 30% improvement in ORR4 in the brentuximab vedotin treatment group, assuming ORR4 for the MTX or bexarotene alone treatment group is 40%. This calculation is based on a 2-sided χ^2 test with a significance level of $\alpha = 0.05$, and a 10% dropout rate using nQuery Advisor 7.0. A minimum of 30 patients (15 per treatment arm) with pcALCL will be included in the study.

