5.8.2.1.2 Key Secondary Efficacy Analysis

Because a fixed sequential testing procedure is used between the primary endpoint and the key secondary endpoints, the key secondary endpoints will be tested only if the primary endpoint is statistically significant. The weighted Holm procedure⁽¹⁾ will be used for testing the key secondary endpoints. See Section 3.2 for details of the statistical decision rules.

Stratified log-rank test statistics will be used to compare PFS between the 2 treatment arms. The hazard ratios along with the 95% CIs will be estimated using a stratified Cox regression model. The Kaplan-Meier method will be used to estimate the distribution of the time-to-event endpoints for each treatment. Median times (if estimable), along with the 2-sided 95% CIs, will be presented.

Assuming the median PFS for the brentuximab vedotin treatment group and the physician's choice treatment group (MTX or bexarotene) are 9 and 6 months, respectively, the number of PFS events is projected to be approximately 101 at the time of the planned final analysis. This is based on an approximately 2-year enrollment period, a dropout rate of 10%, and an α level of 0.01 (2-sided), as specified in Section 3.2 per the weighted Holm procedure.

Comparison of the CR rates between the 2 treatment groups will be conducted using the stratified Cochran-Mantel-Haenszel test. The 95% CI of the difference in the response rates between the 2 treatments will also be provided. No imputation will be conducted for missing data. Patients who do not have any post baseline response assessment as specified in the protocol will be counted as nonresponders.

For skin symptoms (Skindex-29), the primary analysis will be comparing the mean symptom reduction between brentuximab vedotin and the control arms. 'Symptom reduction' is defined for each patient as the maximum reduction from baseline (sum of the 7 items related to skin symptoms normalized to a 1-100 scale). The analysis of covariance (ANCOVA) model controlling for baseline covariates (treatment group, baseline score, disease diagnosis, ECOG) will be employed for the analysis. As a sensitivity analysis, comparison of the 2 treatment groups will be conducted using the linear mixed model with repeated measures at

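### Adverse events are summarised only as crude percentages of patients, although the SAP's own PFS assumption implies roughly 10% to 17% longer time at risk on brentuximab vedotin

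*SAP*

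**What the plan says.** SAP 5.11.1.1 sets the format of the safety tables: "Treatment-emergent AEs (TEAEs) will be tabulated by primary System Organ Class (SOC), High Level Term (HLT), and Preferred Term (PT"). The opening of SAP section 5 makes number and percentage the default for categorical data, and 5.11.1.2 repeats it for SAEs. Protocol 8.1.9 plans tabulations of the same kind. Neither document specifies a person-time rate, a time-to-first-event analysis or a formal between-arm test of adverse events.

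The treatment-emergent window runs from the first dose to 30 days after the last, so its length follows time on treatment. SAP 1.1 links that to progression: "Patients with progressive disease (PD) at any time during the study will be discontinued from study treatment". SAP 5.8.2.1.2 gives the assumed timing of progression: "Assuming the median PFS for the brentuximab vedotin treatment group and the physician's choice treatment group (MTX or bexarotene) are 9 and 6 months", respectively.

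SAP 5.7.2.1 derives treatment duration, treated cycles and dose intensity by drug in the safety population, but no adverse event table uses them. SAP 5.11.1.1 allows extra neuropathy analyses, and SAP 5.11.6 and protocol 8.1.9 allow further safety analyses. All of that wording is optional. Neither document states an expected difference in exposure; the difference discussed here is derived.

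**The concern.** If brentuximab vedotin delays progression as assumed, its patients are treated longer and so watched longer for adverse events. A crude percentage then mixes the hazard of an event with the length of observation. The more the drug delays progression, the more its percentages rise against control even if monthly toxicity is the same. A benefit-risk reading taken from these tables would lean against the longer-treated arm. In an open-label trial, an exposure adjustment chosen after the results are known is also less credible than one fixed beforehand.

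**Working it through.** **Inputs.** Median PFS 9 and 6 months, used as a proxy for time to stopping (SAP 5.8.2.1.2). Treatment cap of 16 three-week cycles or 48 weeks, i.e. 336 days = 11.04 months (SAP 1.1). Window end at last dose + 30 days = 0.99 month (SAP 5.11.1.1). Dosing every 21 days for brentuximab vedotin, weekly for methotrexate, daily for bexarotene with first dose on Day 8 (SAP 5.7.2). Assumptions not in the documents: exponential stopping times and, unless stated, an equal and constant event hazard in both arms.

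**1. Reproduce the plan's own figure.** SAP 5.8.2.1.2 says "the number of PFS events is projected to be approximately 101 at the time of the planned final analysis", using an "approximately 2-year enrollment period, a dropout rate of 10" percent. Protocol 4.3 adds: "The final analyses for the clinical study report will be performed 10 months after the last patient is enrolled". With 62 patients per arm, the event probability per arm is 1 − (e^(−10λ) − e^(−34λ))/(24λ), where λ = ln 2/median. This gives 0.789 and 0.894, so 48.9 + 55.4 = 104.3 events without dropout. With 10% dropout over 34 months it is 102.0, and with 10% per year 98.0. The stated 101 lies between, so the exponential reading of the medians is sound.

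**2. Time at risk if dosing were continuous to progression or week 48.** Mean treatment time = (1 − e^(−λT))/λ with T = 11.04 months.
- Brentuximab vedotin: λ = 0.0770, giving 7.44 months, and 8.42 with the 30 days.
- Control: λ = 0.1155, giving 6.24 months, and 7.22 with the 30 days.
- Ratio 8.42/7.22 = 1.17.

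**3. Time at risk tied to the actual last dose, as the SAP defines it.** Mean last-dose day = d × Σ e^(−λdk), k = 1 to K, where d is the dosing interval in days, λ is per day and K is the maximum number of doses minus 1.
- Brentuximab vedotin (d = 21, K = 15): 211.4 + 30 = 241.4 days = 7.93 months. Undelayed, the sixteenth dose falls at week 45.
- Methotrexate (d = 7, K = 47): 185.4 + 30 = 215.4 days = 7.08 months.
- Bexarotene (daily): 7.20 months, or 6.98 when counted from Day 8.
- Ratios: 7.93/7.08 = 1.12, 7.93/7.20 = 1.10, 7.93/6.98 = 1.14.

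**4. Apparent excess under equal hazard.** With control incidence p and ratio r, excess = [1 − (1 − p)^r] − p. For example, p = 20% and r = 1.166 gives 1 − 0.80^1.166 = 22.9%, an excess of 2.9 points. The ranges below also include the result of averaging over individual exposure times.

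| Control incidence | Continuous dosing (step 2) | Last-dose window (step 3) |
|---|---|---|
| 10% | 1.6 points | 1.0 to 1.3 points |
| 20% | 2.9 to 3.0 | 1.8 to 2.6 |
| 50% | 5.4 to 5.9 | 3.4 to 5.3 |

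If the risk is confined to the first 3 months, the continuous-dosing excess is only 0.5 points at p = 20% and 1.0 at p = 50%.

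**5. Sensitivity to other stopping.** Additional discontinuation of 10% to 50% per year, equal in both arms, leaves the continuous-dosing ratio at 1.16 to 1.14. Unequal stopping matters more: an extra brentuximab vedotin hazard of ln 2/6 − ln 2/9 = 0.0385 per month removes the treatment-time difference.

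**6. Scale against sampling error.** With 62 per arm, the standard error of a difference is √(2 × 0.2 × 0.8/62) = 7.2 points at 20% and √(2 × 0.5 × 0.5/62) = 9.0 points at 50%.

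**The case against.** **No comparison is planned.** The safety objective is to assess the safety of brentuximab vedotin, without the comparison to control that the response, PFS, symptom and EFS objectives carry. The tables have no test, interval or decision rule. This stands, and it limits the point to how readers will interpret two columns side by side.

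**PFS is not time on treatment.** Protocol 7.7 also allows stopping for adverse events, withdrawal and other reasons, and continuation in stable disease is at the investigator's discretion. Toxicity-driven stopping on brentuximab vedotin could close the gap (step 5). Discretionary stopping with fewer control responders (40% against 70% assumed), or delayed cycles running past 48 weeks, could widen it. This stands: the direction is an expectation from the plan's assumptions.

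**The plan already covers it in part.** Exposure is tabulated in the same population, so an imbalance would be visible, and extra analyses are allowed. This stands only partly. A reader cannot derive event-specific time at risk from an exposure table, and the optional wording commits to nothing.

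**Crude incidence answers a legitimate question, and person-time rates can mislead.** Protocol 1.3 and 1.5 describe neuropathy as cumulative. A hazard rising linearly with time (an assumption; cumulative hazard proportional to t², averaged over individual exposure) gives an apparent excess of about 3 to 4 points at 20% and 7 to 9 at 50% on the last-dose windows, so a constant rate describes neuropathy poorly. For early events, such as pancreatitis after one or two doses (protocol 1.5), dividing by longer follow-up makes the brentuximab vedotin rate look 9% to 14% lower (1 − 1/1.10 to 1 − 1/1.17). This stands and shapes the fix.

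**Conclusion.** The point holds as a conditional, minor one. The SAP commits to no exposure-adjusted summary of adverse events, while its window definition, stopping rule and PFS assumption together imply unequal time at risk. The size is 10% to 17% longer on brentuximab vedotin, and 10% to 14% on the SAP's own last-dose definition. Under an equal constant hazard, that is roughly 2 to 6 points of apparent excess for events with control incidence of 20% to 50%, and under 2 points at 10% or less or with early onset. These figures rest on PFS as a proxy for stopping, exponential times and no unequal discontinuation for other reasons.

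A reader might infer a flat 17% and a 3 to 6 point excess for any equally toxic event. The documents do not support that: 17% treats dosing as continuous, whereas the window runs from the last dose of a three-weekly drug, and 3 points or more needs a common event and a sustained hazard. A reader might also infer that the safety comparison is biased by design or that the trial's conclusions are at risk. Neither follows. The exposure difference is not a stated design feature, the effect is smaller than the standard error of a difference, and no efficacy claim or error rate depends on it. It is nevertheless systematic and foreseeable, which justifies a prespecified supplement.

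**What to change.** In SAP 5.11.1.1 and 5.11.1.2, keep the crude percentages and add:

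- Exposure-adjusted first-event rates (patients with a first event per 100 patient-years at risk, with 95% CI) for TEAEs, Grade 3 or higher TEAEs, SAEs and TEAEs leading to discontinuation. Count time at risk from first dose to the first event or the end of the treatment-emergent window, whichever comes first.
- For the peripheral neuropathy SMQ, a time-to-first-event (cumulative incidence) summary by arm, because its hazard is cumulative. Treat the end of the window as censoring and death as a competing event, so the arms are read at the same time since first dose.
- A note that person-time rates assume a roughly constant hazard and can understate early-onset events in the longer-treated arm, so they supplement the percentages and do not replace them.

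The cost is a few extra columns and one summary from event and dosing dates already collected. Conduct, sample size and alpha do not change.
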